3.3.2. Benefit Assessment

Study participants will not benefit directly from involvement in this study. However, the results of this study may contribute significantly to our understanding of changes in intestinal permeability and their relationship to morbidity and mortality in the context of thermal injury. This knowledge is paramount to designing future medicinal interventional studies, aiming to modulate intestinal permeability and, potentially, to improve outcomes for patients following thermal injury.

3.3.3. Overall Benefit:Risk Conclusion

The primary outcome measure of this study is the determination of intestinal permeability in healthy and thermal injury participants. Interventions in this study are the administration of STM by mouth or feeding tube (if one is site for routine clinical care) and the collection of urine and stool samples.

The risk of adverse events is minimised for the population being investigated in the proposed study as no drug intervention will be investigated and study assessments being conducted are non-invasive (with the exception of STM administration and phlebotomy in healthy participants).

4. OBJECTIVES AND ENDPOINTS

Objective	Endpoint
Co-Primary	
1. To determine the impact of thermal injury on the magnitude of small intestinal permeability change as soon as possible following injury compared to healthy participants	
 Lactulose/Mannitol (L/M) ratio at entry
2. To characterise the effect of thermal injury on small intestinal permeability over time and establish the clinical and demographic factors which can influence it	
 Changes in L/M ratio over time
Exploratory	
1. To determine the impact of thermal injury on colonic permeability as soon as possible following injury compared to healthy participants	
 Fractional excretion of sucralose at entry
2. To characterise the effect of thermal injury on colonic permeability over time	
 Changes in the fractional excretion of sucralose over time

Objective	Endpoint
3. To assess the relationship between severity of a participant's condition following thermal injury and changes in intestinal permeability†	
 • Number of ventilator-free days • Number of vasopressor-free days • Number of hemofiltration-free days • Number of episodes of confirmed infection and sepsis • Number of surgical interventions • Total length of hospital stay • Calculate critical care and thermal injury severity scores
4. To assess plasma and urine biomarkers of intestinal permeability, bacterial translocation and renal tubular dysfunction following thermal injury†	
 • Change in markers of intestinal mucosal damage samples from blood • Change in urine protein:creatinine and urine albumin:creatinine ratios
5. To assess the impact of thermal injury and intestinal permeability on the intestinal microbiome compared to healthy participants	
 • Changes in microbiome of acute and convalescent stool samples
6. To assess the impact of pre-existing co-morbid conditions on intestinal permeability and clinical outcome following thermal injury†	
 • Medical history and drug history at the time of admission
7. To assess wound healing	
 • Time to wound recovery (e.g. 95%)
8. To characterise parameters that may influence drug PK/PD†	
 • Determine fluid input/output balance over time • Changes in serum albumin and plasma creatinine
9. To characterise intestinal microbiota, and correlate its composition with both intestinal permeability and bacterial detection in blood†	
 • Changes in intestinal microbiome • Bacterial markers of translocation

[figure not shown]
†Clinical data, routine laboratory results or blood/urine biomarker results obtained from the SIFTI-2 study will be used in the analysis of this exploratory endpoint see Section 5.4.1.

5. STUDY DESIGN

5.1. Overall Design

This is a longitudinal, prospective study of healthy participants and participants who have sustained a thermal injury. The following schematic summarises study measures and their frequency for healthy and thermal injury participants.

Figure 2 Study Schematic

3

5.2. Number of Participants

Table 1 describes the number of participants proposed for the study. Sample size is based on feasibility. No formal calculation of power or sample size has been performed, but a sample size of 15 healthy participants and 25 thermal injury participants ($\geq 15\%$ TBSA) should be sufficient to provide useful estimates of variability in lactulose:manitol ratios, and any change in L/M ratio over time.

Table 1 Recruitment Stratification

	Number of participants
Group 1 Healthy participants	15
Group 2 Thermal Injury participants Percent Total Burn Surface Area (TBSA) ≥15%	25

The healthy participants (Group 1) will be recruited with an age range similar to that typical in thermal injury participants based on historic hospital admission data from the UK and data from the SIFTI1 study [Hampson, 2016].

If participants prematurely discontinue or are withdrawn from the study, additional replacement participants may be recruited at the discretion of the Sponsor in consultation with the investigator see Section 8.2.1.

5.3. Participant and Study Completion

The full duration of the study for healthy participants is approximately two weeks and for thermal injury participants is approximately 6 months.

Thermal injury participants who withdraw prior to week 4 or healthy participants who withdraw prior to week 2 will be considered for analysis, although it is acknowledged that any missing data at later stages of the study may be related to outcome (either positive or negative). Given this is an exploratory study, the impact of missing data will be explored by assessing the sensitivity of results to different missing data approaches (for example, analyse all available data, analyse only complete data across time points and explore imputation of worst or best case scenarios).

Study withdrawals may also include participants who are consented to the study under Section 30 of the Mental Capacity Act 2005. In the event that participants do not re-confirm consent when they regain capacity, they will be withdrawn from the study.

The end of the study is defined as the date of the last visit of the last participant in the study.

5.4. Scientific Rationale for Study Design

5.4.1. Co-recruitment to the SIFTI-2 Study

Thermally injured participants who are eligible for this study must also be eligible for, and enrolled in a partner study named SIFTI-2.

SIFTI-2 is an observational study currently recruiting healthy participants and thermally injured participants and follows a successfully delivered predecessor study SIFTI1 [Hampson, 2016]. The objectives and endpoints of SIFTI-2 are included in the SIFTI-2 study protocol (reference number IRAS ID: 200366). The design of this study has been aligned with the SIFTI-2 study to support the strategy of co-consenting thermally injured participants to both studies. This will reduce the overall impact of research in this population in the following ways:

- There is sufficient residual blood from collection in SIFTI-2 to allow testing of blood biomarkers of interest for the HESTIA study. This strategy therefore limits impact on participants as no additional blood sampling is required for participation in HESTIA (with the exception of HIV, Hepatitis B and C testing at baseline). SIFTI-2 participants will be explicitly consented for their samples and data to be shared in this way.
- Sampling time points and study visits in SIFTI-2 and HESTIA have been aligned to reduce the impact of co-recruitment on thermally injured participants.

[figure not shown]
Clinical data from both studies can be generated from the same participant therefore allowing biomarker, microflora and intestinal permeability data to be compared. In contrast to thermally injured participants, healthy participants enrolling in this study will not be required to co-consent for participation in SIFTI-2.

Data will be shared from the SIFTI-2 study with GSK through a secure electronic database.

A summary of the origin (HESTIA or SIFTI-2) of data and samples collected for the HESTIA study is available in [Appendix 5 Section 12.5](#).

5.4.2. Recruitment and Sampling Schedule

Severely burned patients (with an injury affecting greater than 20% total body surface area), display a significant and rapid increase in intestinal permeability that has been shown to decline over time (Figure 3) [Olquin, 2005]. What is less well understood is whether a greater severity of thermal injury correlates with greater intestinal permeability. Moreover, the time to complete restoration of normal permeability and other factors which may influence permeability (other than the initial injury) are also not well understood.

Figure 3 Burn Injury Results in a Rapid Increase in Intestinal Permeability

This study aims to recruit participants as soon as possible following their admission in order to capture the initial changes in permeability. Serial measurement of intestinal permeability and sampling of the biomarkers of bacterial translocation, intestinal damage and inflammation are required during the acute phase (days 1-14) of admission in order to correlate them with clinical events (e.g. surgery), severity scores and clinical outcomes.

The convalescent time points (28 days and 6 months) are required to determine if intestinal permeability has returned to normal and to correlate observed changes on days 1-14 with longer-term clinical outcomes (e.g. wound healing).

Gut microbiome assessments will be made less frequently than intestinal permeability assessments as changes in the microbiome are predicted to evolve more slowly. Ideally a stool sample will be collected from thermal injury participants at study entry (limited, of course, by when participants first pass stool following admission). A convalescent sample is requested to assess if the gut microbiome is able to restore to a more normal composition (and will be compared with that of healthy participants to make that assessment).

Blood samples (with the exception of HIV, Hepatitis B and Hepatitis C testing at baseline) will not be taken from thermally injured participants during this study. Instead, biomarker data from blood samples taken during the SIFTI-2 study will be used. A single blood draw will be required from healthy participants on day 1 of participation.

5.4.3. Inclusion of Healthy Participants

Patient facing material (i.e. poster) will be used to facilitate recruitment of the healthy participants. Healthy participants will be recruited to this study to provide a baseline for endpoint measures on intestinal permeability and the gut microbiome.

Three measurements of intestinal permeability are required in order to define an average given the variability in healthy participants reported previously. The timing of the replicates follows the intense time course of the study to control for day-to-day variation over a 15 day period.

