10.2. Sample Size Determination

Sample size is based on feasibility. No formal calculation of power or sample size has been performed, but a sample size of 15 healthy participants and 25 thermal injury participants (>15% TBSA) should be sufficient to provide useful estimates of variability in lactulose:mannitol ratios, and any change in L/M ratio over time.

Although the key aim is to estimate the variability and L/M ratio and assess the difference in L/M ratio between thermal injury and healthy participants, for illustration, a trial including 25 thermal injury and 15 healthy participants would have 89% power to detect a 3-fold difference in L/M ratio between thermal injury and healthy participants using a 2-sided significance level of $p < 0.10$. This calculation uses a (log) between-subject SD of 1.15, as estimated from the literature [Olquin, 2005].

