6.1.4. Statistical Analyses / Methods

Endpoints defined in Section 6.1.1 will be summarised by study group, timepoint and visit. Data will summarise mean, standard deviation, standard error, minimum, median, maximum and N.

No formal statistical analysis will be performed.

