10.5. Appendix 5: Derived and Transformed Data

10.5.1. General

Multiple Measurements at One Analysis Time Point

- Mean of the measurements will be calculated and used in any derivation of summary statistics but if listed, all data will be presented.
- If there are two values within a time window the value closest to the target day for that window will be used. If values are the same distance from the target, then the mean will be taken.

Study Day

- Calculated as the number of days from First STM Dose Date:
 - Ref Date = Missing → Study Day = Missing
 - Ref Date < First STM Dose Date → Study Day = Ref Date First STM Dose Date
 - Ref Data ≥ First STM Dose Date → Study Day = Ref Date (First STM Dose Date) + 1

Age

Age = Screening date – Date of Birth
 Date of birth will be imputed based on the assumption that all subjects were born on the 30th June (30 Jun YYYY).

Baux score

Baux score: Age + % Total Body Surface Area (TBSA) burned

10.5.2. **Efficacy**

Fractional Excretion of Lactulose/Mannitol/Sucralose

Data is provided to S&P in the form of quantity of material in micrograms/litre, based on a sample of urine.

Fractional excretion (FE) of lactulose or mannitol or sucralose = (urine concentration (micrograms/litre) × total urine volume excreted in litre) / probe input (micrograms).

Where,

- Urine concentration is provided in the BIOMARKER dataset,
- Urine volumes excreted are provided in the BIOLINK dataset,
- Probe input refers to the total STM taken (as per Table 7.1 of the protocol-5g Lactulose, 2g Mannitol and 2g Sucralose)

Urine concentration in the BIOMARKER dataset will be provided at two timepoints per visit (0-5hr) and (0-24hr)

FE will be calculated for timepoints 0-5 and 0-24 hours for Lactulose, Mannitol and Sucralose.

For calculations of the 0-24 FE's, total urine volume will be based on the following:

Total urine=urine excreted 0-5 hrs + urine excreted 5-24 hours.

Note: If urine excreted 0-5 hrs is missing then total urine should be considered missing.

Note: 1g=1000000 micrograms

L/M ratio

L/M ratio = FE lactulose / FE mannitol

Healthy Participant – Average

• Average = Mean of all data available at all timepoint for each healthy participant.

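### The SAP summarises L/M only on the raw scale, so the variability the protocol set out to estimate is only partly reported and cannot be set directly beside the planning log SD of 1.15

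*Protocol*

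**What the plan says.** **Protocol.** Section 5.4.3 gives two purposes for the repeat tests in healthy participants: "Three measurements of intestinal permeability are required in order to define an average given the variability in healthy participants reported previously", and "The timing of the replicates follows the intense time course of the study to control for day-to-day variation over a 15 day period". Section 10.2 says that "the key aim is to estimate the variability and L/M ratio", together with the difference between burned and healthy participants. Its illustration is that "a trial including 25 thermal injury and 15 healthy participants" "would have 89% power to detect a 3-fold difference in L/M ratio" at a two-sided 0.10 level. The SD used is 1.15 on the log scale, labelled between-subject and taken from the literature. Section 10.6 works on log L/M throughout: summaries by geometric mean and CV, and a repeated-measures model whose covariance structure was to be explored.

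**SAP.** For L/M, section 6.1.4 states: "Data will summarise mean, standard deviation, standard error, minimum, median, maximum and N". It plans no formal analysis. Section 10.5.2 defines the healthy reference: "Average = Mean of all data available at all timepoint for each healthy participant". Appendix 8 lists Table 2.1 (absolute values), Table 2.2 (change from Day 1) and Table 2.3 (% change), by study group and visit. The shell has an SD column and, for healthy participants, an Average row. Individual plots (Figure 2.1) and a full listing of values (Listing 24) are also planned. SAP Table 1, which records departures from the protocol, says that co-primary objective 1 will be summarised without a formal comparison. It does not mention the move from geometric to arithmetic statistics, and it has no row for co-primary objective 2, whose repeated-measures model is also gone.

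**The concern.** L/M is a positive ratio, and the protocol's own planning SD implies strong right skew. An arithmetic SD of such data is driven by a few large values, and it is in different units from the SD the study was planned on. Section 5.4.3 names day-to-day variation as a reason for the design, yet the SAP reports no figure that it identifies as day-to-day (within-subject) variability.

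This matters because the study was meant to inform the design of later studies. With the thermal injury group reduced to 3, repeatability of the test in healthy participants is among the few quantities the data can still estimate with useful precision.

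**Working it through.** **1. The protocol's power figure.** Inputs from protocol 10.2: 25 and 15 participants, ln 3 = 1.0986, log SD 1.15, two-sided 0.10.
- SE = 1.15 × √(1/15 + 1/25) = 0.3756; noncentrality = 1.0986/0.3756 = 2.925.
- Noncentral t with 38 df gives 89.0%; the normal approximation gives 90.0%. The stated 89% reproduces and is not in question.

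**2. What the planned healthy-participant tables contain.** Write σb² and σw² for the between- and within-subject variances on the scale tabulated. With complete data and a random-intercept structure:
- per-visit SD² (Table 2.1) = σb² + σw²
- SD² of the Average row (Table 2.1) = σb² + σw²/3
- SD of change from Day 1 (Table 2.2) = √2 × σw

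So a reader can recover both components, although the SAP does not say so. If the data were normal on the tabulated scale, little would be lost. At an intraclass correlation (ICC) of 0.5, the simulated standard error of the within-subject SD is 0.119 from the two change rows, against 0.104 from a one-way random-effects ANOVA.

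**3. The scale problem.** The tables are on the raw scale. If log L/M is normal with SD 1.15, the raw CV is √(exp(1.15²) − 1) = √(exp(1.3225) − 1) = 1.66, or 166%.

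The documents give no ICC, so one must be assumed. I simulated 15 participants × 3 tests with lognormal values, total log SD 1.15 and ICC 0.5 (20,000 runs):

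| Within-subject SD | 95% range of the estimate | Truth |
|---|---|---|
| Raw scale, from the Table 2.2 change rows | 0.30 to 2.18 × truth (median 0.69) | 1 × |
| Log scale, from ANOVA | 0.61 to 1.02 | 0.81 |

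The log-scale range is 0.61/0.81 = 0.75 to 1.02/0.81 = 1.26 times the truth. On the raw scale a single participant typically supplies 49% of the within-subject variance, against 21% on the log scale. Results at ICC 0.3 and 0.7 are similar.

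**4. Precision a log-scale table would have.** For 15 × 3 there are 30 df within and 14 between subjects. The 95% CI for the within-subject SD runs from √(30/χ²₀.₉₇₅) = 0.80 to √(30/χ²₀.₀₂₅) = 1.34 times the estimate. Taking 1.15 as the total log SD:

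| Assumed ICC | Between SD | Within SD | SD of 3-visit average | 95% range of estimated ICC |
|---|---|---|---|---|
| 0.3 | 0.63 | 0.96 | 0.84 | −0.06 to 0.59 |
| 0.5 | 0.81 | 0.81 | 0.94 | 0.13 to 0.74 |
| 0.7 | 0.96 | 0.63 | 1.03 | 0.39 to 0.85 |

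The within-subject SD is usefully estimated; the ICC is not.

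**The case against.** Much can be said for the SAP. Section 5.4.3 gives the first purpose of the replicates as defining an average, and the SAP derives, tabulates and plots that average. No section of either document asks for a within/between split or an ICC. SDs are reported by group and visit, Table 2.2 carries the SD of change, and Listing 24 gives every value, so log-scale components could be computed later. A reader with Table 2.1 could also compare SD/mean with 166%. The cut to descriptive reporting after termination was deliberate, and Amendment 1 had already dropped the review of healthy L/M data as unlikely to alter the study size.

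Most of this stands, and it rules out two stronger readings. A reader might infer that the key aim goes unanswered. It does not: section 10.2 speaks of variability without asking for its decomposition, and SDs are planned. A reader might also infer that the planned tables cannot resolve the variability a future change endpoint would need, with a sample size uncertain by (1 − 0.3)/(1 − 0.7) = 2.3-fold. But Table 2.2 reports an SD of change, on the raw scale, and the 2.3 comes only from an assumed ICC range of 0.3 to 0.7.

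The objection does not remove the scale point. Conversion from raw summaries relies on lognormality and on SDs that step 3 shows to be unstable. A listing does not commit anyone to report the estimate. The Amendment 1 rationale concerns sizing the thermal injury group, while section 10.2 kept variability in the key aim.

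**Conclusion.** The variability aim is partly met. The SAP moves L/M from the protocol's log-scale summaries to arithmetic ones without recording the change in its own table of departures. As a result no planned summary table can be compared directly with the 1.15, and the within-subject figure that can be recovered is unreliable for data as skewed as the protocol assumed.

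The size rests on four assumptions: 15 evaluable healthy participants with three tests each (the SAP does not state the achieved number, and its Evaluable population may exclude some), lognormal L/M, 1.15 read as the total log SD of one measurement although the protocol labels it between-subject, and an ICC supplied for illustration.

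Severity is minor. The study is exploratory, development of the molecule has ended, and the part of the key aim hit hardest is the group comparison, lost through early termination rather than through this choice.

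**What to change.** In SAP 6.1.4, report geometric mean and CV for L/M, as protocol 10.6 planned. For healthy participants add one descriptive table from a random-intercept model of log(L/M) over Days 1, 8 and 15, fitted separately for the 0-5 h and 0-24 h urine collections. It should give between-subject SD, within-subject SD (or CV) and total log SD, each with a 95% CI, beside the 1.15 from protocol 10.2. An ICC, if shown, needs its interval. In SAP Table 1, list the departure from protocol 10.6: the change of scale and the dropped repeated-measures model.

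The cost is a short addition to the text and one extra table. It needs no new data, and because it is estimation only it is consistent with the SAP's decision not to test hypotheses.

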5.4.4. Preliminary Data Review

A safety review based on raw data will be conducted when approximately 10 participants have completed the study. This review would include data from any participant, either healthy or thermally injured, that has been collected at the time the review is conducted.

5.4.5. The Use of the Sugar Test Materials (Lactulose, Mannitol and Sucralose)

As described in Section 3.2.2, lactulose, mannitol and sucralose will be administered to both thermally injured participants and healthy participants to measure permeability of the small and large intestine. The amount of each of the sugars to be used is based on previous successful clinical studies employing this method and balances having enough sugar present for detection in urine with their potential laxative effect (Del Valle-Pinero, 2013; Doig, 1998; Menzies, 1972).

6. STUDY POPULATION

The study population will comprise healthy and thermal injury participants presenting at enrolling study sites. Please note the following:

- Prospective approval of protocol deviations to recruitment and enrolment criteria, also known as protocol waivers or exemptions, is not permitted.
- Where possible, written informed consent will be obtained from each subject prior to participation in this study. Recruitment of subjects who lack mental capacity is discussed in Section 6.1.
- Healthy participants will be consented to the HESTIA study only.
- Thermally injured participants are required to be co-consented to the SIFTI-2 and HESTIA studies outlined in Section 6.1. A diagrammatic overview of the SIFTI-2 and HESTIA thermal injury participant recruitment is given in Figure 4. (see Appendix 3).

